6.3 MEASURES TO MINIMIZE BIAS: RANDOMIZATION AND BLINDING

Random allocation will be concealed to research staff conducting recruitment and will use a 1:1 allocation with random block sizes of 2 and 4. Block randomization will be achieved with a computer-generated random number list prepared by the study biostatistician having no clinical involvement in the trial. Randomization will be stratified by site (UW vs UCLA) to account for site-specific study characteristics. After the research team member obtains participant consent, they will telephone contact the study project manager who is independent from the recruitment process to receive the group assignment. Alternatively, it may be arranged that randomization will be built into the REDCap database by the study biostatistician.

Since this study aim is feasibility, acceptability and fidelity, there is no plan for whether/when to break randomization codes. Study and clinical team members cannot practically be blinded to treatment because only those randomized to intervention will receive text messages, specific action plans, and coaching. The need for clinical team members to create action plans and interact with coaches will identify those randomized to intervention. Presumably, the need for admission to the hospital for a respiratory illness and secondary clinical endpoints (ED visits, need for antibiotics, steroids, hospital days, and death) are less prone to observer bias. The outcome evaluator (study biostatistician) will remain blinded during analyses.

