9.2 SAMPLE SIZE DETERMINATION

We will enroll a total of 90 participants. Wave 1 will contain 10 participants (5 UW, 5 UCLA); Wave 2 will contain 20 participants (10 UW, 10 UCLA); Wave 3 will contain 60 participants (30 UW, 30 UCLA). Based on this team's preliminary work, eligible children average one severe respiratory illness per year and we estimate 50% of participants will experience at least one respiratory illness during the period of enrollment. We expect to be able to maintain contact and collect data from ≥90% of the participants at the final follow-up, evenly divided between intervention and control groups. We assume this sample will not be powered to establish the efficacy of the intervention; however, it will provide a sufficient sample to determine feasibility and estimate effect sizes which will be used for power calculations in the future large RCT. The following table shows the attainable power levels for detecting various differences in severe respiratory illness rates (primary clinical outcome) between study arms at the two-sided 0.05 significance level, based on a NB regression model with an overdispersion parameter of $\phi=1.0$.

Attainable power levels for detecting differences in severe respiratory illness rates between arms at the two-sided 0.05 significance level based on a NB regression model, assuming a sample size of 45 subjects per arm with a missing value rate of 10% or less.

Relative Risk (RR)	Number of severe respiratory illnesses in intervention arm over 6-month Follow-up period				
	5	10	15	20	25

(Control vs. Intervention) ($\lambda=0.02$)*	($\lambda=0.40$)*	($\lambda=0.06$)*	($\lambda=0.08$)*	($\lambda=0.10$)*
3.0	19%	29%	38%	45%
4.0	31%	41%	59%	68%
5.0	42%	62%	74%	83%

*Severe respiratory illness rate per patient-month

Hence, large effect sizes with RRs ranging between 3.0-5.0 for comparing the severe respiratory illness rates between study arms will be detected with 19-88% power at the two-sided 0.05 significance level.

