9.4 STATISTICAL ANALYSES

9.4.1 GENERAL APPROACH

This section outlines the statistical analysis strategy and procedures for the study. We plan to use the primary outcome data to assess the RE-PACT intervention's feasibility, acceptability, and fidelity. We anticipate being underpowered to assess efficacy using the clinical endpoints of the intervention in this pilot study. The clinical outcome endpoints will be used to develop an estimate of effect size. Categorical variables will be displayed as percentages, and continuous variables as means with standard deviations (if normally distributed) or medians with IQR (if skewed). For inferential statistics, two-sided p-values <0.05 will be considered statistically significant. A detailed Statistical Analysis Plan (SAP) describing all details of the analyses has been developed and will be finalized prior to the database lock and the analysis of the final study data.

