9.4.3 ANALYSIS OF THE SECONDARY ENDPOINT(S)

Clinical Outcomes. We will test differences between treatment (intervention or control) groups in the primary and secondary respiratory illness outcomes. Our goal with these analyses is to estimate effect sizes for the differences between groups which will allow precise sample size calculations for a future large-scale trial.

Primary clinical outcome is the severe respiratory illness rate, defined as the total number of severe respiratory illnesses divided by the person-months over the 6-month follow-up period. The severe respiratory illness rate will be analyzed using a negative binomial (NB) regression model to account for overdispersion in the count data. For the primary analysis, univariate NB regression analysis will be conducted with study arm as a predictor variable. Study site will be included as a stratification factor in the primary analysis to account for stratified randomization. The observed effect size of the analysis will be quantified in terms of relative risk (RR) and reported along with the corresponding 95% confidence interval.

As a secondary analysis, multivariate NB regression analysis will be performed to compare the severe respiratory illness rates between study arms. In this analysis, clinical and demographic characteristics will be included as covariates in an initial non-parsimonious model. The least absolute shrinkage and selection operator (lasso) and elastic net penalty methods for negative binomial regression models will be utilized to identify a parsimonious model with independent covariates. These methods are considered state-of-the art techniques for variable selection (Wang Z., et al. Stat Methods Med Res. 2016).

Longitudinal changes in the severe respiratory illnesses within and between study arms, will be evaluated with generalized linear mixed effects model with a logit link function and subject specific random effects. An autoregressive (AR) correlation structure will be utilized to account for within subject correlations. In this analysis, the presence/absence of severe respiratory illness at the monthly assessments will be the dependent variable, study arm will be included as a predictor variable and study site as a stratification variable to account for the stratified randomization.

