9.4.9 EXPLORATORY ANALYSES

We will test the mediating effect of caregiver capability, opportunity, and motivation (COM-B) measures on the relationship between intervention and respiratory illness outcomes. The mediating effects will be evaluated by conducting a multi-step analysis approach. In the initial step, NB regression analyses will be conducted to examine whether there are differences in respiratory illness outcomes (number of severe respiratory illnesses, systemic steroid courses, systemic antibiotic courses, and respiratory ED visits) between the intervention and control arm, as described in the previous section. In the next step, we will conduct a sequence of univariate analyses, by regressing each potential mediator variable (caregiver capability, opportunity, and COM-B) on the binary study arm variable. If significant associations between the potential mediator variables and study arm are detected, we will regress the respiratory illness outcomes on both the mediator variables and study arm indicator variable using ANCOVA. The

mediation effect for each potential mediator variables will then be tested using the Sobel z-test based on the slope parameter estimates from the corresponding regression models.

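### Section 9.4.9 tests mediation only with the Sobel z, which is strongly conservative at 81 to 90 children, and its ANCOVA step puts the mediated effect on a different scale from the negative binomial arm effect

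*Combined protocol and SAP*

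**What the plan says.** Section 9.4.3 states that the severe respiratory illness rate "will be analyzed using a negative binomial (NB) regression model to account for overdispersion in the count data". Study arm is the predictor, site the stratification factor, and the effect is reported as a relative risk with a 95% interval. The rate is per person-month.

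Section 9.4.9 sets out the mediation analysis in steps:

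1. NB regression of the illness counts on arm.
2. Regression of each candidate mediator on arm.
3. A conditional step: "If significant associations between the potential mediator variables and study arm are detected", then "we will regress the respiratory illness outcomes on both the mediator variables and study arm indicator variable using ANCOVA".
4. A Sobel z-test on the resulting slopes.

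No interval for the mediated effect is planned. No assumed arm-to-mediator or mediator-to-illness effect is given, and no power for mediation. Section 3 lists mediation as a tertiary or exploratory objective. The mediators are FCAT and GSES (capability), FECC (opportunity) and the weekly text-message confidence score (motivation).

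**The concern.** There are two separate points.

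**The test.** The Sobel z treats the product of two estimated slopes as normally distributed. In a small sample the product is not normal, and the test rejects far less often than its nominal level. A mechanism that operates is then more likely to be recorded as absent than it need be with the same data.

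**The scale.** The outcome is modelled as an overdispersed count per person-month in step 1 and as a plain linear outcome in step 3. The total effect is a log rate ratio. The direct and mediator effects are differences in counts, with no exposure term stated, although follow-up can be cut short by withdrawal or loss (sections 7.2 and 7.3). The pieces cannot be put together into a statement of how much of the effect is mediated.

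What is at stake is the yield of an exploratory aim meant to inform the next trial: it would produce a conservative p-value, or nothing at all for a mediator that misses the gate.

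**Working it through.** The plan states no power or error rate for mediation, so there is no figure of its own to reproduce.

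**Inputs from the documents**
- Section 9.2: "We will enroll a total of 90 participants", and power "assuming a sample size of 45 subjects per arm with a missing value rate of 10% or less". This gives 90 × 0.9 = 81 analysed, with 90 as a check.
- Section 6.3: the trial "will use a 1:1 allocation with random block sizes of 2 and 4".
- Section 9.4.1: "two-sided p-values <0.05 will be considered statistically significant".
- Section 9.2: "eligible children average one severe respiratory illness per year", so 1 × 6/12 = 0.5 per child over six months; overdispersion phi = 1.0.

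**Assumptions, not in the documents**
- Arm effect on the mediator, a: 0.3 to 1.0 SD.
- Mediator effect on the log rate, b: -0.26 to -2.2 per SD.
- The 40% lower hospitalization rate from the earlier PACT trial (section 2.2) serves only to anchor scenarios: log(0.6) = -0.51.

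**Step 1. The Sobel statistic itself.** With z_a and z_b the z-values of the two paths,

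z_Sobel = ab / √(a²·SE_b² + b²·SE_a²) = 1 / √(1/z_a² + 1/z_b²).

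This is always smaller in size than the weaker path's z. If the two paths are equally strong, each needs |z| of at least 1.96 × √2 = 2.77 (p about 0.006). Two paths each at p = 0.01 (z = 2.576) give 2.576/√2 = 1.82, p = 0.07. No assumed effect sizes are needed for this step.

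**Step 2. Type I error.** Simulated with n = 81, M = a·arm + N(0,1), and an NB outcome with mean 0.5 and phi = 1.

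| Situation | Planned Sobel + ANCOVA | Both paths significant (joint test) | Monte Carlo product interval |
|---|---|---|---|
| One path null | 0.5–2.0% | 2.3–5.0% | 1.9–4.6% |
| Both paths null | 0.0% | near zero (0.1–0.3%) | near zero |

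**Step 3. Which component costs power.** Model and test were varied separately (n = 81, mean 0.45, phi = 1, 1,000 replicates).

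| a, b | ANCOVA + Sobel | NB + Sobel | ANCOVA + interval | NB + interval |
|---|---|---|---|---|
| 0.5, -0.5 | 19.9% | 19.9% | 38.7% | 38.9% |
| 0.6, -0.6 | 45.2% | 44.9% | 64.1% | 64.7% |
| 0.8, -0.6 | 60.7% | 61.1% | 74.8% | 75.9% |

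Relative loss of the plan against the last column: 1 - 19.9/38.9 = 49%; 1 - 45.2/64.7 = 30%; 1 - 60.7/75.9 = 20%. Changing the model moves power by about 1 point or less. Changing the test moves it by about 14 to 19 points. Separate runs of the first scenario gave 18 to 20% against 37 to 39%. Sobel power was the same with and without the gate, as Step 1 implies: a significant Sobel z already requires a significant arm-to-mediator path.

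**Step 4. Range over assumed effects** (n = 81, mean 0.5, phi = 1).

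For a 40% rate reduction that is half mediated, a × b = -0.51/2 = -0.255:

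| a | Planned | Joint test, NB | Monte Carlo, NB |
|---|---|---|---|
| 0.3 | 12.8% | 24.6% | 19.2% |
| 0.4 | 15.6% | 33.3% | 32.3% |
| 0.5 | 16.3% | 37.9% | 37.4% |
| 0.65 | 17.8% | 36.1% | 32.7% |
| 0.8 | 16.0% | 30.2% | 26.1% |
| 1.0 | 14.6% | 22.1% | 21.4% |

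The loss against the joint test is 34 to 57% (at a = 0.5: 1 - 16.3/37.9 = 57%). With n = 90 and a = 0.5, it is 21.2% against 43.6%, a 51% loss.

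Other scenarios, also against the joint test:
- 40% reduction fully mediated: loss 18 to 29%.
- Relative risk 3 (control vs intervention) fully mediated: loss 5 to 25%.
- Smallest effects tried (a = 0.3, b = -0.3): 1.9% against 8.7%, a 78% loss where every test is weak.

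Simulation error is about 1 point on power and 3 to 5 points on relative loss in the half-mediated scenarios.

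**Step 5. Scale.** In an NB model with a log link, a normal mediator and no arm-by-mediator interaction, the log rate ratio for arm splits as total = direct + a·b. An ANCOVA slope on counts has no such relation to the NB arm effect of step 1 in section 9.4.9.

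**The case against.** The strongest reply is that this is a tertiary analysis in a pilot. The protocol says several times that it expects to be underpowered on clinical outcomes, no decision depends on the mediation result, and no proportion mediated is planned that would combine the two scales. Section 9.4.1 also refers to a detailed SAP still to be made final, which may say more. All of this stands and limits the weight of the point. It does not justify a test that discards information from data already collected when a better one is nearly free.

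A reader might infer several stronger things that the documents do not support:

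- *That moving from NB to ANCOVA loses the power.* Step 3 shows a cost of about 0 to 1 point. The ANCOVA-based interval had 3.4 to 3.7% type I error with one path null, so errors are not inflated either. The case against ANCOVA is scale and exposure.
- *That the significance gate loses power.* For the Sobel test it costs nothing. It matters because a gated-out mediator gets no estimate, and because it would constrain a better test.
- *That the plan loses half its power.* That figure depends on path effects the documents do not give.
- *That the method is why mediation would usually be missed.* In the half-mediated scenarios the joint test still reaches only 22 to 38%, and the interval 19 to 37%. Sample size is the main limit.
- *That two-thirds of counts will be zero.* A mean of 0.5 with phi = 1 gives 1/(1 + 0.5) = 67%, but section 9.2 also expects half the participants to have at least one respiratory illness. No rates are given for the steroid, antibiotic or emergency department outcomes.

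**Conclusion.** The point holds as a low-cost improvement to an exploratory analysis. The Sobel z at 81 to 90 children runs at about 0.5 to 2% instead of 5% when one path is null. The direction of the power loss is certain from the formula. Its size is conditional on assumed path effects: roughly 5 to 25% relative for large effects, about half for modest ones, and more where all tests have little power. The scale mismatch between the NB arm effect and the ANCOVA slopes follows from the text and needs no assumption. The error rates and powers rest on a normal mediator, NB counts with mean 0.45 to 0.5 and phi = 1, and no site effect.

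**What to change.** In section 9.4.9 and the final SAP:

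- Fit the outcome step with the NB model of section 9.4.3, with a log person-months offset and site.
- Replace the Sobel test with a bootstrap or Monte Carlo 95% interval for the indirect effect (the product of coefficients) on the log-rate scale.
- Report it without the significance gate for each mediator measured in both arms: FCAT, GSES and FECC. The text-message confidence score cannot be included: section 4.2 sets up texting only for the intervention arm, so no arm-to-mediator path can be estimated for it under any method.
- Keep the exploratory label and state that power is limited under any test.

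The cost is a change of wording and a few lines of code, with no new data. Section 9.4.1 places the final SAP before database lock, which leaves room for the change.

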10 SUPPORTING DOCUMENTATION AND OPERATIONAL CONSIDERATIONS

10.1 REGULATORY, ETHICAL, AND STUDY OVERSIGHT CONSIDERATIONS

10.1.1 INFORMED CONSENT PROCESS

10.1.1.1 CONSENT/ASSENT AND OTHER INFORMATIONAL DOCUMENTS PROVIDED TO PARTICIPANTS

IRB-approved consent forms in English or Spanish (per participant preference) describing in detail the study intervention, study procedures, and risks are given to the participant and written documentation of informed consent is required prior to starting intervention/administering study intervention.

10.1.1.2 CONSENT PROCEDURES AND DOCUMENTATION

All study participants will undergo informed consent including consent to view the child's medical record. In all informed consent materials, we will make clear to potential participants that their participation is voluntary, and they may choose to leave the study at any time. Potential participants identified from the clinic registry and, following an opportunity to opt-out of further contact, their interest and eligibility will be determined through a structured screening. If a family is interested in participation, they may contact the study team or a member of the study team will contact them for informed consent. Enrollment visits will be conducted either in person or remotely (via WebEx). All consent forms will be signed electronically using a REDCap form. If a family enrolls in person, study staff will supply an iPad on which to sign the consent form. If a family chooses to enroll remotely, study staff will send the family a REDCap survey link containing the consent form. All subjects will also receive a hard copy of the consent form for their records. Informed consent materials will be provided in private spaces in both written and verbal formats, will review in detail the study design, including random assignment to the intervention and control groups, potential risks of participation, protections against risk, and the rights of human research subjects. The informed consent process will also include review and signing of the HIPAA waiver, allowing researchers to review the child's medical records. Parents will be able to decline parts of the study and still participate in other parts, and can revoke their consent at any point.

Because this research involves children with severe cerebral, it is expected that all subjects will lack capacity to give meaningful assent. Assent will not be obtained.

10.1.2 STUDY DISCONTINUATION AND CLOSURE

This study may be temporarily suspended or prematurely terminated if there is sufficient reasonable cause. Written notification, documenting the reason for study suspension or termination, will be provided by the suspending or terminating party. If the study is prematurely terminated or suspended, the Principal Investigator (PI) will promptly inform study participants, the IRB, and sponsor and will provide the reason(s) for the termination or suspension. Study participants will be contacted, as applicable, and be informed of changes to study visit schedule.

Circumstances that may warrant termination or suspension include, but are not limited to:

- Determination of unexpected, significant, or unacceptable risk to participants
- Insufficient compliance of study staff to the protocol (i.e., significant protocol violations)
- Data that are not sufficiently complete and/or evaluable

The study may resume once concerns about safety, protocol compliance, and data quality are addressed, and satisfy the funding agency, sponsor, IRB, or other relevant regulatory or oversight bodies (OHRP, DSMB).

10.1.3 CONFIDENTIALITY AND PRIVACY

Participant confidentiality and privacy is strictly held in trust by the participating investigators, their staff, the safety and oversight monitor(s), and the sponsor(s) and funding agency. This confidentiality is extended to the data being collected as part of this study. Data that could be used to identify a specific study participant will be held in strict confidence within the research team. No personally identifiable information from the study will be released to any unauthorized third party without prior written approval of the sponsor/funding agency.

All research activities will be conducted in as private a setting as possible.

The study monitor, other authorized representatives of the sponsor, representatives of the Institutional Review Board (IRB), and regulatory agencies may inspect all documents and records required to be maintained by the investigator, including but not limited to, medical records for the participants in this study. The clinical study site will permit access to such records.

The study participant's contact information will be securely stored at each clinical site for internal use during the study. At the end of the study, all records will continue to be kept in a secure location for as long a period as dictated by the reviewing IRB, Institutional policies, or sponsor requirements.

Study participant research data, which is for purposes of statistical analysis and scientific reporting, will be transmitted to and stored at the University of Wisconsin. This will not include the participant's contact or identifying information. Rather, individual participants and their research data will be identified by a unique study identification number. The study data entry and study management systems used by clinical sites and by University of Wisconsin research staff will be secured and password protected. At the end of the study, all study databases will be de-identified and archived at the University of Wisconsin.

Measures Taken to Ensure Confidentiality of Data Shared per the NIH Data Sharing Policies. It is NIH policy that the results and accomplishments of the activities that it funds should be made available to the public (see <https://grants.nih.gov/policy/sharing.htm>). The PI will ensure all mechanisms used to share data will include proper plans and safeguards for the protection of privacy, confidentiality, and

security for data dissemination and reuse (e.g., all data will be thoroughly de-identified and will not be traceable to a specific study participant). Plans for archiving and long-term preservation of the data will be implemented, as appropriate.

Certificate of Confidentiality

To further protect the privacy of study participants, the Secretary, Health and Human Services (HHS), has issued a Certificate of Confidentiality (CoC) to all researchers engaged in biomedical, behavioral, clinical or other human subjects research funded wholly or in part by the federal government. Recipients of NIH funding for human subjects research are required to protect identifiable research information from forced disclosure per the terms of the NIH Policy (see <https://humansubjects.nih.gov/coc/index>). As set forth in 45 CFR Part 75.303(a) and NIHGPS Chapter 8.3, recipients conducting NIH-supported research covered by this Policy are required to establish and maintain effective internal controls (e.g., policies and procedures) that provide reasonable assurance that the award is managed in compliance with Federal statutes, regulations, and the terms and conditions of award. It is the NIH policy that investigators and others who have access to research records will not disclose identifying information except when the participant consents or in certain instances when federal, state, or local law or regulation requires disclosure. NIH expects investigators to inform research participants of the protections and the limits to protections provided by a Certificate issued by this Policy.

